1.3. Erdafitinib

Erdafitinib is a potent, oral pan-FGFR tyrosine kinase inhibitor with half maximal inhibitory concentration (IC_{50}) values in the low nanomolar range for all members of the FGFR family (FGFR1 to 4). It has demonstrated potent inhibition of cell proliferation with IC_{50} values ranging from <1 to <130 nM in FGFR pathway-activated cancer cell lines. Erdafitinib has been shown to have in vivo anti-tumor activity in various murine xenograft and patient-derived mouse models of FGFR-driven cancers including gastric, bladder, and others.

In humans, treatment with erdafitinib exhibited dose-related increase in maximum serum concentration (C_{max}) and area under the concentration curve (AUC) and time-independent pharmacokinetics (PK) within the dose range of 0.5 mg to 12 mg, both after single and multiple daily dosing. Median time to maximum serum concentration (T_{max}) observed ranged from 2 to 4 hours (erdafitinib as capsule). Erdafitinib is highly bound to plasma proteins such as α 1-acid glycoprotein (α 1-AGP). In patients, free fractions of erdafitinib in human plasma were small (average ~0.36%). In in vitro experiments, erdafitinib was shown to be a P-glycoprotein (P-gp) substrate and inhibitor.

Only unchanged erdafitinib was present in plasma with no circulating metabolites. The metabolites, mainly N- and O-dealkylated derivatives (M8 and M6, respectively), formed via CYP2C9 and CYP3A enzymes, are efficiently eliminated after their formation in the excreta (majority excreted in feces). Long terminal phase half-life of erdafitinib (>50 hours) in plasma was observed resulting in approximately 3- to 5-fold accumulation of C_{max} and AUC following multiple daily dosing.

The anti-tumor effect of erdafitinib was initially observed both in subjects with urothelial cancer with select FGFR alterations, as well as other solid tumors in the Phase 1 study (Study 42756493EDI1001). Activity and a dose were confirmed in the global Phase 2 trial (Study 42756493BLC2001).

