6.3. Administration of Cetrelimab

In the Phase 1b erdafitinib + cetrelimab cohort and Arm B of Phase 2 (Cycles 1- 4) of the study, cetrelimab will be administered at 240 mg IV Q2W until 1 or more treatment discontinuation criteria are met. The dose of cetrelimab is increased to 480 mg IV Q4W starting at Cycle 5. In the

Phase 1b erdafitinib + cetrelimab + platinum chemotherapy cohort, cetrelimab will be administered at 360 mg IV Q3W until 1 or more treatment discontinuation criteria are met.

The first infusion should be administered over 60 (± 10) minutes. In the absence of infusion-related reactions, subsequent infusions may be administered intravenously over 30 (-5/+10) minutes. Study drug is to be administered under the supervision of site staff. For the first infusion, vital signs should be monitored before the start of the infusion, every 15 to 20 minutes during the infusion, at the end of infusion (EOI), and 2 hours (± 15 min) after the end of infusion. After the completion of the first infusion, the subject may be discharged if considered clinically stable and all other study procedures have been completed. During subsequent infusions of cetrelimab, vital signs should be monitored pre-dose, once during infusion, and at the end of infusion. On days in which both erdafitinib and cetrelimab will be administered, oral erdafitinib should be given before the start of cetrelimab IV infusion. On days in which erdafitinib + cetrelimab + platinum (cisplatin or carboplatin) chemotherapy will be administered, oral erdafitinib should be given prior to cetrelimab, followed by platinum (cisplatin or carboplatin) chemotherapy IV infusion. Refer to the Investigational Product Preparation Instructions (IPPI)/SIPPM for detailed instructions on drug preparation, storage, and administration.

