11.9. Safety Analyses

Adverse Events

The verbatim terms used in the eCRF by investigators to identify AEs will be coded using the most current version of the Medical Dictionary for Regulatory Activities (MedDRA). Toxicities will be graded for severity according to NCI-CTCAE, version 5.0 (see [Table 7](#) for nail toxicity and hyperphosphatemia grading). All reported AEs with onset during the treatment period (ie, TEAEs and AEs that have worsened since baseline) will be included in the analysis.

Specifically, the following will be summarized:

- Incidence of DLT (Phase 1b)
- All AEs, including irAEs
- Grade 3 or higher AEs
- Serious AEs
- AEs leading to permanent discontinuation of treatment
- AEs leading to death

Summaries, listings, datasets, or subject narratives may be provided, as appropriate, for those subjects who die, who discontinue treatment due to an AE, or who experience a severe AE or an SAE.

Clinical Laboratory Tests

Laboratory data will be summarized by type of laboratory test. Reference ranges and markedly abnormal results (specified in the Statistical Analysis Plan) will be used in the summary of laboratory data. Descriptive statistics will be calculated for each laboratory analyte at baseline. Parameters with predefined toxicity grades will be summarized. Change from baseline to the worst Grade experienced by the subject during the study will be provided as shift tables.

Parameters with predefined NCI-CTCAE toxicity grades will be summarized. Change from baseline to the worst AE Grade experienced by the subject during the study will be provided as shift tables.

Vital Signs

Descriptive statistics of pulse/heart rate and blood pressure (systolic and diastolic), and change from baseline will be summarized at each scheduled time point. The percentage of subjects with values beyond clinically important limits will be summarized.

Physical Examination

Frequency tabulations of the abnormalities will be made.

Electrocardiogram

The effects of erdafitinib and cetrelimab on ECGs (QT, QTc, PR, QRS, heart rate) will be evaluated by means of descriptive statistics and frequency tabulations. These tables will include observed values and changes from baseline values to allow detection of clinically relevant changes in individuals.

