^f Subjects on erdafitinib monotherapy (including subjects assigned to Arm A, as well as any subjects who permanently discontinue cetrelimab) do not need to complete the Day 15 visit after Cycle 3. After Cycle 4, subjects continuing on cetrelimab will switch to Q4W dosing and therefore do not need to complete the Day 15 visit procedures.

^g Guidance for study conduct for ongoing subjects in the event of a national disaster is provided in [Attachment 10](#).

^h CrCl is calculated by the Cockcroft-Gault formula ([Attachment 8](#)).

ⁱ Consent for molecular screening (but not full-study screening) may be performed remotely including consent by telephone or video consultation, unless not permitted according to local guidance.

^j Pre-dose only for Arm A.

^k Post-dose ECGs for subjects receiving erdafitinib monotherapy should be recorded 2 to 4 hours after the erdafitinib dose on C2D1 and, if possible, 2 to 4 hours after the erdafitinib dose on C4D1. Post-dose ECGs for subjects receiving erdafitinib and cetrelimab in combination should be recorded as soon as possible upon completion of infusion on C2D1 and C4D1. The End-of-Treatment ECG may be performed at any time during the End-of-Treatment Visit. Additional ECGs may be performed during the study as clinically indicated.

^l Audiometry tests that were performed prior to consent for the full-study was obtained is permitted to be collected as long as it is documented this procedure was performed as part of standard of care and not specifically for study purposes.

Appendix 3 Table 2: Pharmacokinetic, Immunogenicity, and Biomarker Samples for the Phase 2 Erdafitinib +/- Cetrelimab Cohort (Up to and Including Amendment 4)

Assessments/ Procedure	Notes	Molecular Eligibility Screening Period	Full- Study Screening Period	Treatment Cycle 1		Treatment Cycle 2, 3		All Other Cycles		End of Treatment ^a	Follow- up Period ^a
		≥28 days prior to C1D1	Within 28 days prior to C1D1	Day 1	Day 15 (±2)	Day 1 (±2)	Day 15 (±2)	Day 1 (±2)	Day 15 (±2)	Within 30 Days (+7) of last dose	Every 12 weeks
Note: These samples should be drawn on the day study drug is administered. ^b											
Erdafitinib PK ^c (Both Arms)	Pre-dose erdafitinib ^d unless otherwise specified. See Section 9.3.			X	X	Pre-dose erdafitinib C2 & C3; 4h post erdafitinib C2D1 only ^e		Pre-dose erdafitinib C5; 4h post erdafitinib C5D1 only ^e			
Erdafitinib Protein Binding Blood Sample (Both Arms)	4 hrs Post-dose See Section 9.3.					C2D1					

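### On-treatment ECGs run on two clocks: time since erdafitinib in Arm A, end of the cetrelimab infusion in the combination, so ECG timing in the combination is uncontrolled and not like-for-like with Arm A (minor)

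*Protocol*

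**What the plan says.** **Monotherapy.** Footnote k of Appendix 3 Table 1: "Post-dose ECGs for subjects receiving erdafitinib monotherapy should be recorded 2 to 4 hours after the erdafitinib dose on C2D1". The same window applies on C4D1, but only if possible.

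**Combination.** The same footnote, for C2D1 and C4D1: "Post-dose ECGs for subjects receiving erdafitinib and cetrelimab in combination should be recorded as soon as possible upon completion of infusion". Footnote j of Appendix 1 Table 1 carries the same sentence for the Phase 1b erdafitinib + cetrelimab cohort.

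**Dosing order and infusion length (Section 6.3).** On days when both drugs are given, "oral erdafitinib should be given before the start of cetrelimab IV infusion". No minimum or maximum interval is stated there or in Appendix 3 Section 6. For infusion length: "The first infusion should be administered over 60" (±10) minutes, and without infusion reactions "subsequent infusions may be administered intravenously over 30 (-5/+10) minutes".

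**Erdafitinib peak (Section 1.3).** Median Tmax "observed ranged from 2 to 4 hours (erdafitinib as capsule"). The study itself uses tablets.

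**Use of the ECGs (Section 11.9).** ECG effects are described with summary statistics and frequency tables: "These tables will include observed values and changes from baseline values to allow detection of clinically relevant changes in individuals".

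The Phase 2 schedule points to Section 9.6.5 for exact ECG timing, and Section 9.6.5 points back to the schedule. The footnotes are therefore the only timing rule.

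**The concern.** The Arm A window coincides with the stated erdafitinib peak. The combination rule ignores erdafitinib and follows the infused drug. C2D1 and C4D1 are the only scheduled on-treatment ECGs, and the End-of-Treatment ECG may be taken at any time in that visit. If erdafitinib is swallowed just before the infusion starts, the combination is read early in the absorption phase while Arm A is read around the peak. Side-by-side QTc summaries would then mix a treatment difference with a timing difference. With prompt dosing that timing difference has one direction: the combination is read earlier relative to the peak.

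The rule covers about 45 Arm B subjects and the 12 to 30 expected in the Phase 1b erdafitinib + cetrelimab cohort. Safety of both regimens is part of the Phase 2 primary objective, although the primary safety endpoint is adverse event incidence, not QTc.

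**Working it through.** **Step 1: when the combination ECG can fall.** Time after erdafitinib = gap from erdafitinib to infusion start + infusion length. Section 6.3 gives 30 − 5 = 25 to 30 + 10 = 40 minutes for later infusions and 60 ± 10 = 50 to 70 minutes for the first. The later length applies to C2D1 and C4D1 in Arm B and the standard Phase 1b regimen. In the alternative regimen cetrelimab starts on C2D1, so the first-infusion length applies to that visit. The gaps are assumed, because the protocol gives none.

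| Assumed gap (min) | End of later infusion (min after erdafitinib) | End of first infusion (min after erdafitinib) |
|---|---|---|
| 0 | 25–40 | 50–70 |
| 15 | 40–55 | 65–85 |
| 30 | 55–70 | 80–100 |
| 60 | 85–100 | 110–130 |

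Section 9.6.5 asks for 5 minutes' rest and triplicate tracings 5 minutes apart, so the last tracing comes about 5 + 2 × 5 = 15 minutes later. With no gap and a later infusion that is 40 to 55 minutes after erdafitinib, still under an hour. Arm A is read at 120 to 240 minutes.

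To reach 120 minutes at the end of a later infusion, the gap must be 120 − 40 = 80 to 120 − 25 = 95 minutes. For a first infusion it must be 120 − 70 = 50 to 120 − 50 = 70 minutes. Nothing in the protocol requires either.

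**Step 2: how much concentration this costs.** Section 1.3 gives a terminal half-life above 50 hours and 3- to 5-fold accumulation. With k = ln 2 / half-life and daily dosing, accumulation = 1/(1 − e^(−24k)). A half-life of 50 h gives 3.5 and 75 h gives 5.0, both inside the stated range. Three-fold accumulation would need 24 × ln 2 / ln 1.5 = 41 h, below the stated half-life, so it was not modelled.

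The assumed model is one-compartment oral dosing at steady state: C(t) ∝ ka/(ka − k) × [e^(−kt)/(1 − e^(−24k)) − e^(−ka·t)/(1 − e^(−24ka))]. The absorption rate ka is not in the protocol. Values of 0.8 to 2.0 per hour were assumed because they give a Tmax of about 1.9 to 3.6 h. Concentration as a fraction of peak:

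| Half-life, ka | Tmax | 0 min | 25 min | 40 min | 120 min | 240 min |
|---|---|---|---|---|---|---|
| 50 h, 0.8/h | 3.55 h | 0.77 | 0.85 | 0.88 | 0.98 | 1.00 |
| 50 h, 2.0/h | 1.87 h | 0.74 | 0.90 | 0.95 | 1.00 | 0.98 |
| 75 h, 0.8/h | 3.60 h | 0.84 | 0.89 | 0.92 | 0.98 | 1.00 |
| 75 h, 2.0/h | 1.89 h | 0.82 | 0.93 | 0.96 | 1.00 | 0.99 |

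At 25 to 40 minutes the concentration is 0.85 to 0.96 of peak, so about 4 to 15% below it. At the two ends of the Arm A window it is 0.98 to 1.00.

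**Step 3: the other difference between arms.** Arm A may be up-titrated to 9 mg while Arm B stays at 8 mg (Appendix 3 Table 3). That is (9 − 8)/8 = 12.5% more dose in Arm A, similar in size to the timing effect, in the same direction, and untouched by any change in ECG timing.

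**The case against.** The strongest reply is that early timing is possible but not prescribed. No maximum gap is set, and footnote e of Appendix 3 Table 2 allows erdafitinib PK samples to be drawn during the cetrelimab infusion. On C2D1 the only post-dose erdafitinib sample is the 4-hour one, so the protocol contemplates an infusion still running 4 hours after the dose. That would put the ECG at or after the Arm A window. This stands. A reader might infer that combination ECGs are always taken before the peak, but the documents support only that they can be. The same latitude also means that the timing varies without control.

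A reader might also infer a shortfall of 20 to 33%, from trough/peak = 1 − 1/R with R = 5 or 3. That treats absorption as instantaneous at the peak and absent at 25 to 40 minutes, and R = 3 does not fit a half-life above 50 h. The figure does not hold.

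Other points that stand:
- Arm A's C4D1 window is not firm.
- The Tmax is for the capsule.
- Shorter later infusions are optional and depend on no infusion reaction.
- Section 11.9 plans no formal comparison of ECGs between arms, and extra ECGs are allowed when clinically indicated.
- An end-of-infusion ECG is a reasonable choice for looking at the infused drug.

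None of this gives the combination ECG a defined time after erdafitinib.

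**Conclusion.** The point holds as a minor scheduling inconsistency. Monotherapy ECGs are tied to erdafitinib. Combination ECGs are not, and a compliant one can fall 25 to 40 minutes after the dose (50 to 70 minutes on C2D1 in the alternative regimen). QTc summaries for the two arms are therefore not read at a common time.

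The likely size is modest: roughly 4 to 15% below peak concentration with no gap before a later infusion, and less with longer gaps. This rests on a one-compartment model, half-lives of 50 to 75 h, assumed absorption rates, and tablets behaving like the capsule.

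A reader might go further and infer that a QTc prolongation in the combination would be missed, or that timing alone explains any difference between arms. The documents do not support either. They report no QTc prolongation with erdafitinib and no concentration–QTc relation, and the list of potential risks in Table 3 has no QT item. QT-prolonging agents appear only among the concomitant medications to avoid or use with caution. The 8 mg versus up-titrated 9 mg difference would remain even with identical timing.

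**What to change.** Reconcile footnote k (Appendix 3 Table 1) and footnote j (Appendix 1 Table 1) to one rule: record the C2D1 and C4D1 ECGs 2 to 4 hours after the erdafitinib dose in all subjects and, in combination subjects, also after the infusion has ended. Footnote i of Appendix 2 Table 1 repeats the combination sentence and should be read for consistency at the same time. The circular reference between the Phase 2 schedule and Section 9.6.5 can be closed in the same edit.

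The cost is footnote wording and no extra ECG. On C2D1 the ECG fits before the 4-hour erdafitinib PK sample already scheduled in both arms. On C4D1 a combination subject dosed just before a later infusion would wait a further 80 to 95 minutes, so about 1 to 2 hours.

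The schedule for the period after data collection ends (Appendix 4) contains no ECG, so for many subjects the remedy lies in the analysis. Where ECG times are available, summarise QTc and its change from baseline by actual time since the erdafitinib dose. Section 7 already has the time of supervised dosing recorded in the eCRF. Where ECG times are not available, say next to any side-by-side display of the arms that ECG timing differed by design.

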1. INTRODUCTION

Refer to Section 1 of the protocol for the introduction. The introduction includes a description of urothelial bladder cancer, FGFR signaling, erdafitinib, PD-1/PD-L1 signaling, cetrelimab (summary of nonclinical data, summary of clinical data), platinum chemotherapy in metastatic urothelial cancer, overall rationale for the study, the anticipated benefits and risks for erdafitinib and cetrelimab, and the anticipated benefits and risks for platinum chemotherapy.

2. OBJECTIVES, ENDPOINTS, AND HYPOTHESIS

2.1. Objectives and Endpoints for Phase 2 (Dose Expansion)

Objectives	Endpoints
Primary	

 To evaluate the safety and clinical activity of erdafitinib alone and in combination with cetrelimab in cisplatin-ineligible subjects with metastatic or locally advanced urothelial cancer with select FGFR gene alterations and no prior systemic therapy for metastatic disease 	
 Overall response rate (ORR) (partial response [PR] or better) per Response Evaluation Criteria in Solid Tumors (RECIST) 1.1 by investigator assessment Incidence of adverse events (AEs)
Secondary	

 To characterize the PK of erdafitinib and cetrelimab To assess the immunogenicity of cetrelimab To further assess safety at the R2PD of erdafitinib alone and in combination with cetrelimab To further characterize the clinical activity of erdafitinib alone and in combination with cetrelimab 	
 Plasma erdafitinib and serum cetrelimab concentrations Detection of antibodies to cetrelimab and effects on serum cetrelimab levels Incidence of AEs, serious adverse events (SAEs) and laboratory values Duration of response (DoR) Time to response (TTR) Progression-free survival (PFS) OS
Exploratory	

 To assess the expression of CCI To evaluate changes in CCI To assess changes in CCI To explore biomarkers (DNA, RNA, and/or protein) in tissue and blood samples that could CCI To explore the relationships between PK, PD, AE profiles, and CCI 	

2.2. Hypothesis

Erdafitinib alone and in combination with cetrelimab are safe and have anti-tumor activity in cisplatin-ineligible subjects with metastatic or locally advanced urothelial cancer with select FGFR gene alterations and no prior systemic therapy for metastatic disease.

3. STUDY DESIGN AND RATIONALE

3.1. Overview of Study Design

Refer to Section 3.1 of the main body of the protocol.

3.1.1. Phase 1b

Not applicable to the Phase 2 erdafitinib +/- cetrelimab cohort.

3.1.2. Phase 2: Erdafitinib +/- Cetrelimab Cohort

An overview of the Phase 2 dose expansion cohort is described in [Figure 3](#).

In Phase 2 (dose expansion), approximately 90 subjects with metastatic or locally advanced urothelial cancer with select FGFR gene alterations based on molecular testing who meet the definition of cisplatin-ineligible and have not had prior systemic therapy for metastatic disease will be stratified by ECOG PS (0-1 versus 2) and then assigned randomly (1:1 ratio) to either the erdafitinib monotherapy treatment (Arm A), or the combination treatment of erdafitinib and cetrelimab (Arm B). To further characterize safety and clinical activity of the erdafitinib and cetrelimab (Arm B).

A DRC will be commissioned for Phase 2 of this study. Based on emerging safety data, on 12 May 2020, the DRC recommended to remove the requirement for up-titration from the erdafitinib + cetrelimab combination. The DRC also made a recommendation to close Dose level 2 in Phase 1b and focus enrollment efforts into the Phase 2 part of the study. Therefore, Arm B will no longer include up-titration for erdafitinib.

Refer to [Section 11.10](#) of the main body of the protocol and the DRC charter for details regarding the composition and scope of the DRC.

Refer to [Appendix 3 Table 3](#) for an overview of the Phase 2 dosing administration of erdafitinib and cetrelimab.

3.2. Study Design and Starting Dose Rationale

Refer to Section 3.2 of the main body of the protocol.

3.3. Dose-Limiting Toxicity Evaluation and Determination of RP2D

Not applicable to the Phase 2 erdafitinib +/- cetrelimab cohort.

3.4. Study Evaluation Team

Not applicable to the Phase 2 erdafitinib +/- cetrelimab cohort.

4. SUBJECT POPULATION

Adult subjects age 18 years and older with metastatic or locally advanced urothelial cancer who meet the molecular eligibility and full-study eligibility are eligible for the study. Screening

assessments will be performed as indicated in the Phase 2 erdafitinib +/- cetrelimab Time and Events Schedule [Appendix 3 Table 1](#). Molecular eligibility assessment may occur ≥ 28 days prior to administration of the study drugs.

The inclusion and exclusion criteria for enrolling subjects in this study are described in the following 2 subsections. If there is a question about the inclusion or exclusion criteria below, the investigator should consult with the appropriate sponsor representative before enrolling a subject in the study. For a discussion of the statistical considerations of subject selection, refer to Section [11.1](#), Sample Size Determination.

4.1. Inclusion Criteria

Each potential subject must satisfy all of the following criteria to be enrolled in the study:

1. ≥ 18 years of age.
2. Criterion modified per Amendment 2
 - 2.1 Histologic demonstration of transitional cell carcinoma of the urothelium. Variant urothelial carcinoma histologies such as glandular or squamous differentiation, or evolution to more aggressive phenotypes such as sarcomatoid or micropapillary change are acceptable.
3. Criterion modified per Amendment 2
 - 3.1 Metastatic or locally advanced urothelial cancer (Stage IV disease per AJCC Staging Guidelines)
4. Criterion modified per Amendment 2
 - 4.1 Criterion modified per Amendment 3
 - 4.2 Phase 1b erdafitinib + cetrelimab cohort and **Phase 2:** Meet appropriate molecular eligibility criteria. Tumors must have at least one gene fusion or gene mutation as defined in [Table 4](#).
5. Criterion modified per Amendment 2
 - 5.1 Must have measurable disease by radiological imaging according to the Response Evaluation Criteria in Solid Tumors (RECIST, version 1.1) at baseline.
6. Criterion modified per Amendment 2
 - 6.1 Criterion modified per Amendment 3
 - 6.2 Prior systemic therapy for metastatic urothelial cancer:
 - Phase 1b erdafitinib + cetrelimab cohort:

- Any number of lines of prior therapy
- Renal function for subjects must have a creatinine clearance (CrCl) ≥ 30 mL/min as calculated by Cockcroft-Gault ([Attachment 8](#))
- Phase 1b erdafitinib + cetrelimab + platinum chemotherapy cohort:
 - No prior systemic therapy for metastatic disease. **Note:** Subjects who received neoadjuvant or adjuvant chemotherapy and showed disease progression, within 12 months of the last dose are considered to have received systemic chemotherapy in the metastatic setting
 - Renal function for subjects must have a creatinine clearance (CrCl) ≥ 30 mL/min to receive carboplatin and ≥ 60 mL/min to receive cisplatin as calculated by Cockcroft-Gault ([Attachment 8](#))
- **Phase 2:**
 - No prior systemic therapy for metastatic disease. **Note:** Subjects who received neoadjuvant or adjuvant chemotherapy and showed disease progression, within 12 months of the last dose are considered to have received systemic chemotherapy in the metastatic setting.
 - Cisplatin-ineligible based on:
 - ECOG PS 0-1 AND at least one of the following criteria:
 - Renal function defined as creatinine clearance (CrCl) < 60 mL/min as calculated by Cockcroft-Gault ([Attachment 8](#)) ([Galsky 2011](#))
 - Grade 2 or higher peripheral neuropathy per NCI-CTCAE version 5.0.
 - Grade 2 or higher hearing loss per NCI-CTCAE version 5.0,
- **OR**
 - ECOG PS 2

7. Criterion modified per Amendment 2

7.1 Criterion modified per Amendment 3

7.2 ECOG PS Grade of (see [Attachment 3](#)) as defined below:

Phase 1b erdafitinib + cetrelimab cohort: ECOG 0-2

Phase 1b erdafitinib + cetrelimab + platinum chemotherapy cohort: ECOG 0-1 for cisplatin and ECOG 0-2 for carboplatin.

Phase 2: ECOG 0-2

8. Criterion modified per Amendment 1

8.1 Criterion modified per Amendment 2

8.2 Criterion modified per Amendment 3

8.3 Adequate organ function at Screening defined as follows:

- Phase 1b erdafitinib + cetrelimab cohort and **Phase 2**

Hematology	
Bone marrow function (without the support of cytokines or erythropoiesis-stimulating agent in preceding 2 weeks)	
Hemoglobin	$\geq 8.0 \text{ g/dL} (\geq 5 \text{ mmol/L})$ (without transfusion or demonstrate stability, ie; no significant decline in hemoglobin, for 2 weeks after transfusion)
Platelets	$\geq 75 \times 10^9/\text{L}$
Absolute Neutrophil Count (ANC)	$\geq 1.5 \times 10^9/\text{L}$
Chemistry	
AST and ALT	$\leq 2.5 \times$ upper limit of normal (ULN) or $\leq 5 \times$ ULN for subjects with liver metastases
Creatinine clearance (mL/min)	Calculated using the Cockcroft-Gault formula (Attachment 8) Phase 1b erdafitinib + cetrelimab cohort: $\geq 30 \text{ mL/min}$ Phase 2: $\geq 30 \text{ mL/min}$. If the subject is considered cisplatin-ineligible based on creatinine clearance then CrCl must also be $< 60 \text{ mL/min}$.
Total bilirubin	$\leq 1.5 \times$ ULN or direct bilirubin \leq ULN for subjects with total bilirubin levels $> 1.5 \times$ ULN
Thyroid panel: TSH, T3 or Free T3 (FT3) and Free thyroxine (FT4)	All within normal range. If TSH is not within normal limits, the subject may still be eligible if total T3 or free T3 and free T4 are within normal limits.
Phosphate	Below institutional ULN within 14 days of treatment and prior to C1D1 (medical management allowed)
Cardiovascular	
Left ventricular ejection fraction	Within normal institutional limits

Abbreviations: ALT=alanine aminotransferase; ANC=absolute neutrophil count; AST=aspartate aminotransferase; QTcF=QT corrected interval by the Fridericia's formula; ULN=upper limit of normal

Phase 1b erdafitinib + cetrelimab + platinum (cisplatin or carboplatin) chemotherapy cohort

Hematology	
Bone marrow function (without the support of cytokines or erythropoiesis-stimulating agent in preceding 2 weeks)	
Hemoglobin	$\geq 9.0 \text{ g/dL}$ ($\geq 5.59 \text{ mmol/L}$) (without transfusion or demonstrate stability, ie; no significant decline in hemoglobin, for 2 weeks after transfusion)
Platelets	$\geq 100 \times 10^9/\text{L}$
Absolute Neutrophil Count (ANC)	$\geq 1.5 \times 10^9/\text{L}$
Chemistry	
AST and ALT	$\leq 2.5 \times$ upper limit of normal (ULN) or $\leq 5 \times$ ULN for subjects with liver metastases
Creatinine clearance (mL/min)	Calculated using the Cockcroft-Gault formula (Attachment 8) Phase 1b erdafitinib + cetrelimab + platinum chemotherapy cohort: $\geq 30 \text{ mL/min}$ to receive carboplatin and $\geq 60 \text{ mL/min}$ to receive cisplatin
Total bilirubin	$\leq 1.5 \times$ ULN or direct bilirubin \leq ULN for subjects with total bilirubin levels $>1.5 \times$ ULN
Thyroid panel: TSH, T3 or Free T3 (FT3) and Free thyroxine (FT4)	All within normal range. If TSH is not within normal limits, the subject may still be eligible if total T3 or free T3 and free T4 are within normal limits.
Phosphate	Below institutional ULN within 14 days of treatment and prior to C1D1 (medical management allowed)
Cardiovascular	
Left ventricular ejection fraction	Within normal institutional limits

Abbreviations: ALT=alanine aminotransferase; ANC=absolute neutrophil count; AST=aspartate aminotransferase; QTcF=QT corrected interval by the Fridericia's formula; ULN=upper limit of normal

9. Criterion modified per Amendment 2

9.1 Criterion modified per Amendment 1.

9.2 Criterion modified per Amendment 3

